10.6 Analyses

Two main sets of analyses for all endpoints are proposed. The first limits assessment to data from periods 1 and 2, and the second uses data from all periods. The first set will summarize data based upon differences between period endpoints, with comparisons by arm. The second will employ repeated measure models to estimate period effects.

For fractions 2-5, adverse events will be summarized by frequency and severity and packing type. For the ordinal measures, mean differences and 95% confidence intervals for the difference will be calculated by packing type. Repeated measure models will be used to describe treatment' effects over time and F-tests will be used to assess period affects. Graphical methods will aid in assessing model assumptions.

11 REGULATORY AND OPERATIONAL CONSIDERATIONS

11.1 Regulatory and Ethical Considerations

11.1.1 Informed Consent Document

Consent forms will be written in accord with federal regulations and will be reviewed and approved by the UVA IRB-HSR prior to use. Signed consent forms and other research records will be retained in a confidential manner.

11.1.2 Consent Procedures and Documentation

Informed consent is a process that is initiated prior to the individual's agreeing to participate in the study and continues throughout the individual's study participation. Consent forms will be Institutional Review Board (IRB)-approved and the participant will be asked to read and review the document. A member of the study team will explain the research study to the participant and answer any questions that may arise. A verbal explanation will be provided in terms suited to the participant's comprehension of the purposes, procedures, and potential risks of the study and of their rights as research participants. Participants will have the opportunity to carefully review the written consent form and ask questions prior to signing. The participants should have the opportunity to

discuss the study with their family or surrogates or think about it prior to agreeing to participate. The participant will sign the informed consent document prior to any procedures being done specifically for the study. Results from procedures completed prior to consent for standard of care purposes may be used for research purposes. Participants must be informed that participation is voluntary and that they may withdraw from the study at any time, without prejudice. A copy of the informed consent document will be given to the participants for their records. The informed consent process will be conducted and documented in the source document (including the date), and the form signed, before the participant undergoes any study-specific procedures. The rights and welfare of the participants will be protected by emphasizing to them that the quality of their medical care will not be adversely affected if they decline to participate in this study.

Version Date: 11/16/2021

Doctors and physicists who plan to complete the Physician and Physicist Assessment Surveys are considered participants. A member of the study team will explain the research study and allow the individual to review the protocol. Doctor and physicist participants must be informed that participation is voluntary and that they may withdraw from the study at any time, without prejudice. Doctors and physicists will give verbal consent to participate.

11.1.3 Confidentiality and Privacy

Participant confidentiality and privacy is strictly held in trust by the participating investigators, their staff, and the sponsor(s) and their interventions. This confidentiality is extended to cover testing of biological samples and genetic tests in addition to the clinical information relating to participants. Therefore, the study protocol, documentation, data, and all other information generated will be held in strict confidence. Consents will be maintained in a confidential manner in accordance with the code of federal regulations and HIPAA. When possible, specimens will be coded with IDs (not MRN or name). No information concerning the study or the data will be released to any unauthorized third party without prior written approval of the sponsor.

All research activities will be conducted in as private a setting as possible.

The study monitor, other authorized representatives of the sponsor, representatives of the Institutional Review Board (IRB), regulatory agencies or pharmaceutical company supplying study product may inspect all documents and records required to be maintained by the investigator, including but not limited to, medical records (office, clinic, or hospital) and pharmacy records for the participants in this study. The clinical study site will permit access to such records.

The study participant's contact information will be securely stored at each clinical site for internal use during the study. At the end of the study, all records will continue to be kept in a secure location for as long a period as dictated by the reviewing IRB, Institutional policies, or sponsor requirements.

Study participant research data, which is for purposes of statistical analysis and scientific reporting, will be entered and stored in the designated EDC System. This will include limited participant identifying information, including participants' initials and dates of birth. Individual participants and their research data will be identified by a unique study identification number. The study data entry and study management systems used by clinical sites and UVA CC research staff will be secured and password protected.

Certificate of Confidentiality

To further protect the privacy of study participants, a site may apply for a Certificate of Confidentiality. For NIH studies, this will automatically be issued by the National Institutes of Health (NIH) and an application is not necessary. This certificate protects identifiable research information from forced disclosure. It allows the investigator and others who have access to research records to refuse to disclose identifying information on research participation in any civil, criminal, administrative, legislative, or other proceeding, whether at the federal, state, or local level. By protecting researchers and institutions from being compelled to disclose information that would identify research participants, Certificates of Confidentiality help achieve the research objectives and promote participation in studies by helping assure confidentiality and privacy to participants.

Version Date: 11/16/2021

11.1.4 Safety Oversight

The University of Virginia Cancer Center Data and Safety Monitoring Committee (CC DSMC) will provide oversight of the conduct of this study. The CC DSMC will report to the UVA Protocol Review Committee (PRC).

The UVA CC DSMC will review the following:

- All adverse events
- Audit results
- Application of study designed stopping/decision rules
- Whether the study accrual pattern warrants continuation/action
- Protocol violations

The UVA CC DSMC will meet every month for aggregate review of data. Tracking reports of the meetings are available to the PI for review. Issues of immediate concern by the DSMC are brought to the attention of the sponsor (and if appropriate to the PRC and IRB) and a formal response from the sponsor is requested. Per the UVA Cancer Center NIH approved institutional plan, this study will be audited approximately every 6 months. The audit may include direct access to source data/documents.

Any study under the purview of the University of Virginia IRB-HSR is subject to review of files at the University of Virginia. Studies are chosen for Post-approval Monitoring either a) at random or b) requested by a study team member or any member of the IRB-HSR.

The purpose of Post-approval Monitoring audits is to ensure that documentation of clinical research studies is of the highest quality, verify protocol adherence, and ensure that all Federal and local rules concerning clinical research are being fulfilled. Post-approval monitoring is done by staff within the office of the Vice President for Research (VPR) in accordance with their Standard Operating Procedures. The conduct of an on-site review may include but is not limited to:

- requests for progress reports from investigators,
- examinations of research records, including signed informed consent documents, protocol modifications, and unexpected, serious, and/or related adverse experience reports,
- contacts with research subjects, or
- observation of the consent process and/or research procedures. Examples of when observation of the consent process could occur are:

 Full board IRB determines during review of a project that a conflict of interest exists such that the informed consent process should be observed by a neutral party;

Version Date: 11/16/2021

- IRB is made aware of a complaint or concern with regard to the informed consent process; or
- IRB determines as a result of the monitoring process that the consent process is insufficient and education/training is required for conduct of consent.

Limited monitoring will be conducted by a quality assurance team at the Allegheny Health Network. This includes the following patient related data such as eligibility review and data source verification. SAEs will also be reviewed by a safety team at the Allegheny Health Network

The quality assurance team does not review:

- contacts with research subjects, or
- observation of the consent process and/or research procedures. Examples of when observation of the consent process could occur are:
 - Full board IRB determines during review of a project that a conflict of interest exists such that the informed consent process should be observed by a neutral party;
 - IRB is made aware of a complaint or concern with regard to the informed consent process; or
 - IRB determines as a result of the monitoring process that the consent process is insufficient and education/training is required for conduct of consent.

11.1.5 Site Monitoring

Clinical site monitoring is conducted to ensure that the rights and well-being of trial participants are protected, that the reported trial data are accurate, complete, and verifiable, and that the conduct of the trial is in compliance with the currently approved protocol/amendment(s), with International Conference on Harmonisation Good Clinical Practice (ICH GCP), and with applicable regulatory requirement(s).

- The UVA Coordinating Center will implement ongoing monitoring activities
 for this study to ensure that Participating Institutions are complying with
 regulatory and protocol requirements, data quality, and subject safety.
 Monitoring will occur before the clinical phase of the protocol begins,
 continue during protocol performance and through study completion.
- Monitoring may be conducted either remotely or on-site. For remote visits, each institution will be required to provide redacted source documents for review or appropriate access to the EMR. The UVA CC will provide the Participating Institution with a follow-up letter following completion of the monitoring visit which should be maintained in the site regulatory files. The schedule for monitoring may be adjusted according to subject accrual and data quality. The Investigator will be notified in advance of each visit.
- Independent audits may be conducted by each institution according to institutional guidelines. Results of these audits may be requested by the UVA Coordinating Center.

11.1.6 Quality Assurance and Quality Control

Each clinical site will perform internal quality management of study conduct, data and biological specimen collection, documentation and completion according to institutional policies.

Version Date: 11/16/2021

Quality control (QC) procedures will be implemented beginning with the data entry system and data QC checks that will be run on the database will be generated. Any missing data or data anomalies will be communicated to the site(s) for clarification/resolution.

Following written Standard Operating Procedures (SOPs), the monitors will verify that the clinical trial is conducted and data are generated and biological specimens are collected, documented (recorded), and reported in compliance with the protocol, International Conference on Harmonisation Good Clinical Practice (ICH GCP), and applicable regulatory requirements.

The investigational site will provide direct access to all trial related sites, source data/documents, and reports for the purpose of monitoring and auditing by the sponsor, and inspection by local and regulatory authorities.

11.2 Data Handling and Record Keeping

11.2.1 Data Collection and Management Responsibilities

Data collection is the responsibility of the clinical trial staff at the site under the supervision of the site investigator. The investigator is responsible for ensuring the accuracy, completeness, legibility, and timeliness of the data reported.

All source documents should be completed in a neat, legible manner to ensure accurate interpretation of data.

Data will be collected using a password-protected, centralized electronic case report form system. Data recorded in the electronic case report form (eCRF) derived from source documents should be consistent with the data recorded on the source documents.

11.2.2 Study Records Retention

Study documents should be retained for a minimum of 2 years after the date of the release for commercial distribution by the manufacturer or until at least 2 years have elapsed since the formal discontinuation of clinical development of the study intervention. These documents should be retained for a longer period, however, if required by local regulations. No records will be destroyed without the written consent of the sponsor, if applicable. It is the responsibility of the sponsor to inform the investigator when these documents no longer need to be retained. Record retention will be in accord with 21 CFR 62 and HIPAA regulations.

11.3 Publication and Data Sharing Policy

This study will be conducted in accordance with the following publication and data sharing policies and regulations:

National Institutes of Health (NIH) Public Access Policy, which ensures that the public has access to the published results of NIH funded research. It requires scientists to submit final peer-reviewed journal manuscripts that arise from NIH funds to the digital archive PubMed Central upon acceptance for publication.

11.4 Conflict of Interest Policy

The independence of this study from any actual or perceived influence, such as by industry, is critical. Therefore, any actual conflict of interest of persons who have a role in the design, conduct, analysis, publication, or any aspect of this trial will be disclosed and managed. Furthermore, persons who have a perceived conflict of interest will be required to have such conflicts managed in a way that is appropriate to their participation in the design and conduct of this trial. The study leadership in conjunction with the institution has established policies and procedures for all study group members to disclose all conflicts of interest and will establish a mechanism for the management of all reported dualities of interest.

[name], an investigator for this study, is also the chief medical officer and founder of Brachyfoam, the manufacturer of the BrachyGel Vaginal Hydrogel Packing System used in this study. He will serve as a resource for study design and planning, but will not enroll patients, or supervise any students or trainees involved in research on this project as pertains to the data collection and analysis of results. He will administer brachytherapy during about half of the fractions administered at UVA. When he administers brachytherapy, he will not complete the physician questionnaire. In these instances, [name] will complete the part of the questionnaire related to completeness and imaging clarity of packing and the question related to ease of use will be left blank.

13 APPENDICES

13.1 Schedule of Activities (SoA)

| Procedures | Screening (within 6 weeks of Brachytherapy 1) | Brachytherapy 1 | Brachytherapy 2 | Brachytherapy 3 | Brachytherapy 4 | Brachytherapy 5 | 30 Day +/- 2 weeks Safety Follow-up |
|---|---|-----------------|-----------------------|-----------------|-----------------|-----------------|---|
| Informed consent | Х | | | | | | |
| Demographics | Х | | | | | | |
| Baseline conditions/assessment | X ² | | | | | | |
| Randomization | | | X ⁵ | | | | |
| Brachytherapy ¹ | | X^4 | Χ | Χ | Χ | Χ | |
| Physical exam | X ² | | | | | | X |
| Performance status | X ² | | | | | | X |
| Concomitant medications related to pain control during procedure ⁷ | | | Х | Х | Х | Х | |
| Physician Assessments of imaging/packing experience | | | Х | Х | Х | Х | |
| Physicist Assessments of imaging/packing experience | | X ⁶ | Х | Х | Х | Х | |
| Participant survey ³ | | | Х | Х | Х | Х | |
| Adverse event review and evaluation | | | X | | | X | Х |

Version Date: 11/16/2021

¹ Alternations will be based on Arm Assignment according to *Figure 1*.

² Must occur within 30 days of Brachytherapy 1. The assessments can be collected on the same day as Brachytherapy 1.

³ Participant survey should be completed without 1 hour following removal of packing after completion of brachytherapy. Not collected if participant was sedated.

⁴ Brachytherapy 1 is considered to be a part of the screening visit. Brachytherapy 2 is considered to be the "start of treatment." Brachytherapy 1 must occur within 14 days of registration.

⁵ No sooner than 10 days before Brachytherapy 2.

⁶ Only the dosimetry measurements need to be collected for Brachytherapy 1.

⁷ Not collected if participant was sedated.

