| | To estimate the difference in physician-scored use experience between BrachyGel and standard vaginal packing. | Physician-scored use experience scored on a 4-point scale for periods 1 through 4 (e.g. fractions 2 through 5). |
| Study Population: | Adult women with locally advanced cervical cancer (FIGO Stages IB1-IVB) for whom brachytherapy boost is planned using intracavitary high-dose rate brachytherapy as part of definitive radiation therapy. | |
| Description of Sites/Facilities Enrolling Participants: | Participants will be enrolled at the University of Virginia and at the Allegheny Health Network | |
| Description of Study Intervention: | Participants will receive brachytherapy according to clinical care and will alternate between standard packing and BrachyGel packing. The order of alternation will vary between Arms A and B. | |
| Study Duration: | Accrual should be completed within 14 months and data collection and analysis will take after 12 additional months (total of 26 months). | |

| Participant Duration: | Each participant will receive 5 fractions of brachytherapy, each about |
|-----------------------|--|
| | 2-7 days apart, followed by a 30 day safety visit. |
| | |

Version Date: 11/16/2021

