9.1.5 Time Period and Frequency for Event Assessment and Follow-Up

The occurrence of an adverse event (AE) or serious adverse event (SAE) may come to the attention of study personnel during study visits and interviews of a study participant presenting for medical care, or upon review by a study monitor.

All AEs including local and systemic reactions not meeting the criteria for SAEs will be captured on the appropriate case report form (CRF). Information to be collected includes event description, time of onset, clinician's assessment of severity, relationship to study product (assessed only by those with the training and authority to make a diagnosis), and time of resolution/stabilization of the event. All AEs occurring while on study must be documented appropriately regardless of relationship. All AEs will be followed to adequate resolution.

Any medical condition that is present at the time that the participant is screened will be considered as baseline and not reported as an AE. However, if the study participant's condition deteriorates at any time during the study, it will be recorded as an AE.

Changes in the severity of an AE will be documented to allow an assessment of the duration of the event at each level of severity to be performed. AEs characterized as intermittent require documentation of onset and duration of each episode.

Version Date: 11/16/2021

Study staff will record all reportable events with start dates occurring any time after brachytherapy fraction 2 is completed until 30 days (for non-serious AEs) or anytime (for SAEs considered related to the study intervention) after the last day of study treatment. At each study visit, the investigator will inquire about the occurrence of AE/SAEs since the last visit. Events will be followed for outcome information until resolution or stabilization.

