10.5 Safety Monitoring

All study participants who receive treatment will be assessed for the occurrence of treatment related adverse events. Adverse events of potential concern related to the vaginal packing, are acute vaginal adverse events (aVAE) which: i) is determined to be at least possibly related to BrachyGel; ii) occurs within the first 30 days from 1st Brachytherapy treatment utilizing BrachyGel (ie. Period 2 or 3 depending on the randomization arm); and iii) meets the criterion below:

Has any of the following vaginal toxicities grade >= 3 according to CTCAE:

- Vaginal pain
- Vaginal perforation
- Vaginal hemorrhage
- Vaginal inflammation
- Vaginal infection
- Dyspareunia

Safety will be assessed by monitoring the number of participants who experience an aVAE. Results reported in Romano et al 2017 on high-dose brachytherapy experience at UVA noted that 0/74 = 0% (upper limit of 95% CI of 4.9%) patients experienced grade ≥3 aVAE.²⁰ Others have reported similarly low rates with at most 2% for late vaginal toxicity.^{21,22} For this study the upper boundary of a sequential probability ratio test (SPRT) based upon a binomial test of proportions for aVAE will be used for monitoring, to protect against excessive aVAE rates. The stopping boundary is for a SPRT contrasting a null 4% versus an unacceptable 9% aVAE rate, with nominal type I and II errors of 10% and 10%, respectively. The slope of the parallel line for monitoring is 2.54 and the intercept is 0.062.

Safety stopping guidelines for the occurrence of aVAEs are detailed in the following table. If a stopping bound is crossed then accrual to the study will be suspended until the study PI, co-investigators and the DSMC can review the data, and determine if the study should continue, be amended or be closed to further accrual.

| Number of participants who received BrachyGel | Number with grade ≥ 3 aVAE | | |
|---|----------------------------|--|--|
| 3-7 | ≥ 3 | | |
| 8-23 | ≥ 4 | | |
| 24-39 | ≥ 5 | | |
| 40-45 | ≥ 6 | | |

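### The safety visit may fall up to 14 days before the 30-day adverse event window closes, and no later inquiry is scheduled

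*Combined protocol and SAP*

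**What the plan says.** The last column of the Schedule of Activities (section 13.1) is headed "30 Day +/- 2 weeks Safety Follow-up". The row "Adverse event review and evaluation" is marked at Brachytherapy 2, at Brachytherapy 5 and at this visit. No call or visit follows.

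The heading does not say from which day the 30 days run. The synopsis (section 1.1) describes fractions "2-7 days apart, followed by a 30 day safety visit", which points to the last fraction.

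Section 9.1.5 sets the recording period for event onset: "until 30 days (for non-serious AEs) or anytime (for SAEs considered related to the study intervention) after the last day of study treatment". On how events are found, it says: "At each study visit, the investigator will inquire about the occurrence of AE/SAEs since the last visit". It also accepts that events may come to light "during study visits and interviews of a study participant presenting for medical care, or upon review by a study monitor".

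Section 10.5 uses a second 30-day window with a different start. An acute vaginal adverse event (aVAE) counts towards the stopping boundary if it is grade 3 or higher, is judged at least possibly related to the gel, and "occurs within the first 30 days from 1st Brachytherapy treatment utilizing BrachyGel".

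**The concern.** The visit window in 13.1 does not secure the recording window in 9.1.5. A site can follow the schedule exactly, see the participant on day 16, and have no further planned occasion to ask about the rest of the 30 days. Questioning at visits looks back, so a visit on day 16 cannot pick up an event that starts on day 20.

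What is at stake is the safety description of a device that, according to section 2.2.5, has not yet been used in living patients. Frequency, intensity and duration of adverse events form a secondary endpoint (section 3). If the last inquiry can fall anywhere from day 16 to day 44, the observed event rate depends partly on when each participant happened to be seen. The aVAE count in 10.5 is exposed in the same way, though less often.

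**Working it through.** The plan gives no figure of its own to reproduce. The check is calendar arithmetic.

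**Inputs**

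- Safety visit: nominal day 30, tolerance 14 days (13.1), counted from the last fraction.
- Recording window for non-serious events: 30 days after the last study treatment (9.1.5).
- Interval between fractions, *g*: 2 to 7 days (1.1).
- First gel fraction: fraction 3 in Arm A, fraction 2 in Arm B (6.1).
- aVAE window: 30 days from the first gel fraction (10.5).

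**Step 1. Permitted visit days.** Earliest: 30 − 14 = day 16. Latest: 30 + 14 = day 44.

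**Step 2. Uncovered part of the general window.** For a visit on day *v*, uncovered days = max(0, 30 − *v*).

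| Visit day | Uncovered days |
|---|---|
| 16 | 14 |
| 20 | 10 |
| 23 | 7 |
| 25 | 5 |
| 28 | 2 |
| 30 or later | 0 |

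The worst case is days 17 to 30: 14/30 = 47% of the window. It is the same in both arms, because the window starts from the last treatment.

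**Step 3. Uncovered part of the aVAE window.** With five fractions, there are *k* = 2 intervals from first gel to fraction 5 in Arm A and *k* = 3 in Arm B. The visit falls *k* × *g* + *v* days after first gel, so uncovered days = max(0, 30 − *k* × *g* − *v*). With *v* = 16:

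| Interval *g* | Arm A: visit day after first gel | Arm A: uncovered | Arm B: visit day after first gel | Arm B: uncovered |
|---|---|---|---|---|
| 2 | 2×2 + 16 = 20 | 10 | 3×2 + 16 = 22 | 8 |
| 3 | 2×3 + 16 = 22 | 8 | 3×3 + 16 = 25 | 5 |
| 5 | 2×5 + 16 = 26 | 4 | 3×5 + 16 = 31 | 0 |
| 7 | 2×7 + 16 = 30 | 0 | 3×7 + 16 = 37 | 0 |

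**Step 4. When the aVAE gap disappears.** At the shortest spacing (*g* = 2), the window is covered by a visit on or after day 26 in Arm A (4 + 26 = 30) or day 24 in Arm B (6 + 24 = 30). With a day-16 visit, Arm B is covered once the mean interval reaches 14/3 ≈ 4.7 days, and Arm A only at 14/2 = 7 days. A shortfall therefore needs an early visit together with short spacing.

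**Step 5. Treatment that ends early.** Step 3 assumes five fractions. If treatment stopped at fraction 3, *k* would be 0 in Arm A, and a day-16 visit would leave 30 − 16 = 14 aVAE days uncovered. In Arm B *k* would be 1, leaving 30 − 2 − 16 = 12 days at 2-day spacing and 30 − 7 − 16 = 7 days at 7-day spacing.

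**The case against.** The strongest reply is that the gap lies in scheduled visits, not in the duty to record. Section 9.1.5 obliges staff to record events with onset up to day 30 whenever the visit falls. It names routes other than visits (presentation for care and monitor review), and it sets no time limit for related serious events. This stands, and it narrows the exposed set to mainly non-serious events, starting after an early visit, for which the participant does not seek care. It does not close the gap, since a monitor can find only what someone has documented.

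Three stronger readings are tempting, and the documents support none of them.

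- *That the gel would look safer than standard packing.* Each arm has two gel and two standard fractions among fractions 2 to 5. Arm A ends on gel, Arm B ends on standard packing (6.1), and allocation is equal (10.2). Events are summarised by packing type (10.6). Events missed after fraction 5 would follow both packing types about equally, so no direction between them follows.
- *That the difference between 10 and 8 uncovered days biases an arm comparison.* The arms are sequences, not treatments. The boundary in 10.5 counts all gel recipients together and does not compare arms.
- *That the stopping boundary fails.* An aVAE is at least grade 3 and so is more likely than a mild event to reach staff through medical care. If it is also serious and related, it is recordable at any time. The documents give no distribution of onset times from which a loss of sensitivity could be calculated.

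It can also be said that a symmetric tolerance is an ordinary scheduling choice, that no section requires this visit to close the window, and that a later contact might be described in the Study Reference Manual, which was not available for this review. All of this is fair. The protocol itself still contains no step that secures its own 30-day window.

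**Conclusion.** The mismatch between 13.1 and 9.1.5 holds, and it is minor. A compliant visit can leave up to 14 of 30 days (47%) of the non-serious event window without scheduled inquiry; a visit on or after day 30 leaves none. With five fractions 2 to 7 days apart, up to 10 days (Arm A) or 8 days (Arm B) of the aVAE window can be uncovered.

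The likely effect is some understatement of absolute adverse event rates and, less often, of the aVAE count. Its size in events cannot be derived from the documents. The primary D2cc comparison is untouched.

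The conclusion assumes that the 30 days in 13.1 run from the last fraction, and that no later contact is arranged outside the protocol. The aVAE figures also assume that first gel use follows section 6.1.

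**What to change.** Reconcile section 13.1 with 9.1.5 so that the last scheduled adverse event inquiry cannot precede day 30 after the last fraction, and state that anchor in the column heading. The simplest form is a late-only tolerance: 30 days, +2 weeks, so day 30 to day 44. An alternative is to keep the present window and add a telephone check on or after day 30 for anyone seen earlier.

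Either leaves max(0, 30 − 30) = 0 uncovered days. It also covers the aVAE window, because the first gel fraction is never later than the last fraction, so that window closes by day 30 at the latest.

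The cost is one changed heading and slightly less scheduling flexibility, or one extra call per early visit. Treatment, sample size and analysis do not change.
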